# 9.2. Schedule of Events

Each subject's participation will be comprised of the scheduled visits listed in Section 9.2 over the course of approximately 4-5 months during the run-in period and study period. The continued access period may lengthen the overall duration of the study considerably. Refer to the Appendices (Section 18.4) for the Visit Details Table.

With sponsor approval, telemedicine (e.g., remote/virtual visit) may be performed for office visits that do not require any of the following:

- Collection of blood test samples.
- Training
- Device related procedures that require staff assistance

# 9.3. Study Visit Schedule & Scheduled Follow-Up Visit Windows

### Run-in Period Visits: To be completed in 45 days

- Screening Visit 1 (Office): Consent and Screening
- Run-in Visit 2 (Office): Day 7 after Visit 1 (+3 days)
  - Eligibility has been confirmed
  - Start Study Pump
    - Pump Training
  - Start CGM (if using SAP prior to Screening)
    - If SAP using Suspend on Low/Predictive Suspend before Low prior to Screening, those features may be used from Visit 2
    - CGM Training, if applicable
- Run-in Visit 3 (Office): Day 0 after Visit 2 (+7 days)
  - Start CGM (if not already started at Visit 2)
  - Start 2 weeks of measured sensor wear period
    - System is used in manual Mode by subjects who are not using Auto Mode with 670G at Screening
      - SmartGuard™ features (Suspend on Low, Predictive Suspend before Low) may be activated
    - SAP subjects using Auto Mode with 670G at Screening may use Auto Mode:
      - Auto Correction must be turned off
      - Auto Basal setpoint must be set to 120 mg/dL
- Run-in Visit 4: Office Visit Day 14 after Visit 3 (+7 days)
  - Confirm run-in CGM data:
    - Subject demonstrates sensor compliance (i.e. 3,225 glucose sensor data points equivalent to 11.2 days of sensor wear)
  - Continue using study pump with CGM

CIP321 Clinical Investigation Plan				
10813115DOC	Version D	Page 59 of 118		Medtronic

- SmartGuard™ features (Suspend on Low, Predictive Suspend before Low) may be activated
- SAP subjects using Auto Mode with 670G at Screening may use Auto Mode:
  - Auto Correction must be turned off
  - Auto Basal setpoint must be set to 120 mg/dL

### **Study Period Visits:**

- Visit 5: Office Visit 7-14 days after Visit 4
  - Start AHCL (e.g. Auto Mode feature turned ON with auto-correction)
- Visit 6: Telephone Visit (option of office visit) Day 1 after Visit 5
- Visit 7: Telephone Visit (option of office visit) Day 2 after Visit 5
- Visit 8: Telephone Visit (option of office visit) Day 3 after Visit 5
- Visit 9: Telephone Visit (option of office visit) Day 4 after Visit 5
- Visit 10: Telephone Visit (option of office visit) Day 5 after Visit 5
- Visit 11: Telephone Visit (option of office visit) Day 6 after Visit 5
- Visit 12: Telephone Visit (option of office visit) Day 7 after Visit 5
- Visit 13: Office Visit Day 14 after Visit 5 (± 3 days)
- Visit 14: Telephone Visit Day 21 after Visit 5 (± 3 days)
- Visit 15: Office Visit Day 30 after Visit 5 (± 5 days)
  - Visit 16: Telephone Visit (option of office visit) Day 45 after Visit 5 (± 5 days) • Change Glucose Target
- Visit 17: Office Visit Day 60 after Visit 5 (± 7 days)
  - Visit 18: Office Visit Day 90 after Visit 5  $(\pm 7 \text{ days})$ 
    - End of Study (EOS) Period

### **Continued Access Period Visits:**

•

- Continued access visits will take place at 90 day (± 14 days) intervals from the last study period visit (Visit 18) – Office or Telemedicine Visit.
  - If the subject is entering continued access directly from the study period, Visit 18 and the first continued access visit may occur on the same day.
  - If the subject has previously completed the study period and exited the study, continued access visits will begin following the signing of the current ICF/Assent.
  - Subjects are instructed to continue uploading study device data weekly
    - It is recommended that an HbA1c sample is drawn and tested at each quarterly visit. If drawn, the test must be run by the Central lab.
- 780G system use Start Office Visit or Telemedicine Visit
  - Start of 780G system use
  - Dispense 780G system
  - Train subjects on 780G system use
  - Start SmartGuard™ (Auto Mode) with all features turned on
- 780G Telephone Visit
  - Day 1 after 780G System use Start Visit
    - Check for adverse events
    - Check for device deficiencies
    - o Review CareLink data

10813	115DOC
-------	--------

- 780G Telephone Visit
  - Day 3 after 780G System use Start Visit
    - Check for adverse events
    - $\circ \quad \text{Check for device deficiencies} \\$
    - Review CareLink data
- 780G Telephone Visit -
  - Day 7 after 780G System use Start Visit (± 2 days)
    - Check for adverse events
    - Check for device deficiencies
    - Review CareLink data
- 780G Telephone Visit -
  - Day 15 after 780G System use Start Visit (± 3 days)
    - Check for adverse events
    - Check for device deficiencies
- 780G Office or Telemedicine Visit
  - Day 30 after 780G System use Start Visit (+ 7 days)
    - Check for adverse events
    - Check for device deficiencies
- Subsequent visits following receipt of the 780G system will take place at 90 day intervals (± 14 days) from the initial 780G visit (780G system use start) until Sponsor announces the end of the study. The subject will remain on the 780G system for the remainder of the Continued Access Period. These visits can be Office or Telemedicine Visits.
  - Subjects are instructed to continue uploading study device data weekly
    - It is recommended that an HbA1c sample is drawn and tested at each quarterly visit. If drawn, the test must be run by the Central lab.

# CIP321 Clinical Investigation Plan Medtronic 10813115DOC Version D Page 61 of 118

### Figure 4. Visit Schedule

# 9.4. Subject Consent

Informed Consent/Assent will be obtained in accordance with the Code of Federal Regulations (CFR) Title 21, Part 50. Prior to entry into the study, the California Experimental Subject Bill of Rights (if applicable), the Institutional Review Board (IRB) and Medtronic approved ICF/Assent form and an Authorization Form required by the Health Insurance Portability and Accountability Act (HIPAA) will be presented to each subject to review and sign as applicable. The subject or parent/guardian will be offered the opportunity to review these documents away from the investigational center. Consent by a legal guardian or authorized representative is only allowed for subjects who are younger than legal age according to their state requirements.

The following will be provided to or explained to the subject or parent/guardian by the investigator or designee: The purpose of the study, the duration of the study, the requirements expected to be adhered to by the subject during the study and the potential risks /possible benefits associated with participation in the study. Every attempt will be made to answer the subject or parent/guardian's questions during the informed consent/assent process. The language used shall be as non-technical as possible and must be understandable to the subject or parent/guardian.

Neither the investigator, nor the investigation site staff shall coerce or unduly influence a subject or parent/guardian to participate or to continue to participate in the clinical study. The informed consent/assent process shall not waive or appear to waive the subject's rights.

# (

CIP321 Clinical Investigation Plan				
10813115DOC	Version D	Page 62 of 118		Medtronic

Subjects will complete California Experimental Subject's Bill of Rights (if applicable), the HIPAA Form, and the ICF/Assent form. The consenting process must be documented in the subject's source files. The subject or parent/guardian will receive copies of the fully executed documents. A subject's participation in study procedures cannot begin before the consent process has been properly executed.

Medtronic will inform the investigators whenever information becomes available that may be relevant to the subject's confirmed participation in the clinical study. The investigator or his/her authorized designee should inform the subject or parent/guardian in a timely manner.

Medtronic will revise the written ICF/Assent form whenever new information becomes available that may be relevant to the subject's confirmed participation in the clinical study, as well as at the time of initiating the continued access period. The revised information will be sent to the investigator for approval by the IRB. After approval by the IRB, a copy of this information must be provided to the participating subjects, and the informed consent/assent process as described above needs to be repeated.

If the ICF/Assent form is amended during the course of the study, the IRB will determine:

- Whether or not active subjects should be re-consented at their next visit and •
- Whether or not subjects who have completed the study at the time of the amendment should repeat the informed consent/assent process.

Subjects will be informed that qualified personnel from the investigational center, the sponsor (Medtronic), agencies such as the FDA and/or the IRB, may have access to the clinic records that reveal their identity and health care information.

The investigational center must report the following informed consent/assent violations to their IRB and sponsor:

- Failure to obtain informed consent/assent from subject.
- Failure to obtain informed consent/assent prior to performing one or more study procedures.
- Failure to maintain ICFs/Assent forms on file for all subjects who have provided informed • consent.
- Use of an ICF/Assent form that has not received approval from the IRB.
- Use of an incorrect version of the ICF/Assent form.

10813115DOC

# 9.5. Assessment of Safety

AE information is collected in this study. See Section 11 for further information regarding the collection of AEs and safety information.

# 9.6. Medical Oversight

In order to conduct the study, investigational center staff that have the appropriate medical training is required.

# 9.6.1. Medical Staff

A physician (or designee) who has managed patients on both CGM and insulin pump therapy will be included in the study as the principal investigator.

### 9.6.2. Qualification

The investigator (or designee) will need to have one of the following qualifications: Endocrinology fellowship or management in patients with diabetes in a clinical practice. The provider must be qualified to treat diabetic emergencies.

### 9.6.3. Experience

Investigator (or designee) must also have at least one-year experience in managing patients with insulin carbohydrate ratios and insulin sensitivity ratios in his/her practice

# 9.7. Safety Monitoring/Risk Analysis

### 9.7.1. Glucose Monitoring Risk

- Subjects will be instructed to make sure they have clean fingers when performing finger stick glucose testing.
- Subjects will have training on diabetes self-management principles.

# 9.7.2. Hypoglycemic/Hyperglycemic Risk

Intervention and treatment for hypoglycemia and hyperglycemia is addressed in Section 10.

# 9.7.3. Calibration of CGM Risk

When an erroneous glucose value is used to calibrate a CGM, the bias is carried through until the next opportunity to calibrate the CGM. This can result in an incorrect bias. Subjects will be trained to appropriate calibration.

Page 63 of 118

Version D

10813115DOC

Version D

Page 64 of 118

# 9.7.4. Reuse Risk

All study devices will be single patient use.

# 9.7.5. Sterilization Risk

The following devices will be supplied sterilized:

- Infusion sets
- Insulin reservoirs
- Glucose sensors

# 9.7.6. Misuse Risk

Comprehensive training will take place at the initiation visit for investigational center staff regarding the operation of the AHCL, to include all of its functional components and all other study devices to be used during the study at the investigational center.

# 9.7.7. Risk of Blood Sample Collection, Contamination from Sampling Techniques

Detailed mitigations to blood sampling risk are provided in Section 10.

# 9.7.8. HbA1c Risk

A Central laboratory will be used for HbA1c testing. HbA1c is the primary safety endpoint.

# 9.8. Glucose and Glycemia Measurements

During the course of the study, the subjects' BG levels, SG levels, HbA1c, and blood ketones will be assessed using the methods outlined in this section.

# 9.8.1. Daily Blood Glucose

Values will be assessed during the study by all subjects using the CONTOUR®NEXT LINK 2.4 study meter/ Accu-Chek™\* Guide Link study meter. The control solution test will be performed following the manufacturer's user guide. Subjects will be trained on the use of the CONTOUR®NEXT LINK 2.4 study meter/ Accu-Chek™\* Guide Link study meter per the manufacturer's instructions.

# 9.8.2. Blood Ketone Values

Blood ketones will be measured by all subjects using the Precision Xtra™\* ketone meter when certain conditions are met. The control solution test will be performed following the manufacturer's user guide. The investigational center staff will be trained on the use of the Precision Xtra™\* ketone meter per the manufacturer's instructions. All ketone measurements will be reported by study subjects.

CIP321 Clinical Investigation Plan				
10813115DOC	Version D	Page 65 of 118		Medtronic

**Note:** In the event the blood ketone meter is not used by subjects to collect ketone values, urine ketones should be measured and reported

# 9.8.3. Sensor Glucose Values

SG data will be collected by subject's study pump and calibrated by each subject's CONTOUR®NEXT LINK 2.4 study meter/ Accu-Chek™\* Guide Link study meter.

# 9.8.4. **HbA1c**

Collected at baseline, the first HbA1c value, will be used as demographic information. HbA1c is also collected at the end of subjects' participation during study period, during continued access period (see Visit Details table for schedule) and at the end of subject's participation during continued access period.

# 9.9. Recording Data

Data will be captured on eCRFs using OC-RDC module. Original eCRFs will not be considered as source data and supporting documentation will be required.

Electronic device data will be collected from the study pump using CareLink™ Personal software and CareLink™ system software. The system uses TLS technology, which encrypts all data it stores (21 CFR Part 11 compliant). Certain data points stored in the downloaded information may also be captured on the appropriate eCRF. Electronic device data could also be collected by the Clinical App and the CareLink™ Clinical App.

The investigator will ensure that all eCRFs are completed promptly, completely, and accurately. Medtronic will provide detailed instructions to assist with eCRF completion. In the event of data discrepancies, investigational centers will be asked to resolve queries electronically in the OC-RDC system; otherwise, irresolvable data-related issues will be routed to the sponsor for review and final disposition. An audit trail is maintained in OC-RDC to capture any corrections or changes of the eCRFs. System backups for data stored in the Oracle Clinical system will be consistent with Medtronic Standard Operating Procedures (SOPs).

Medtronic will only consider eCRFs to be complete when all discrepancies between source data and eCRF have been resolved and eCRF content has been reviewed by a study monitor. In addition, specific eCRFs must also be reviewed and electronically signed by the investigator, indicating his/her agreement with the accuracy of all recorded data. It is expected that the investigator and his/her staff will cooperate with the monitoring team and provide any missing data in a timely manner.

# 9.10. Deviation Handling

A deviation is any instance(s) of failure to follow, intentionally or unintentionally, the requirements of the CIP. It is expected that the investigator will conduct this clinical trial in compliance with the CIP and all applicable regulations governing the conduct of clinical research involving human subjects. Failure to do so could result in one or all of the following:

- Investigational center disqualification
- Notification to the regulatory authorities/IRB depending on the severity of the deviation and reporting requirements

10813115DOC

Version D Page 66 of 118 Medtronic

The investigator should not implement any deviation from, or changes to, the CIP without agreement by the sponsor and prior review and documented approval/favorable opinion from the IRB, except where necessary to eliminate an immediate hazard(s) to trial subjects or when the change does not affect the scientific soundness of the plan or the rights, safety, and welfare of the subjects.

The following are deviations related to study procedures:

- If subject is not compliant with his/her SMBG and pump uploads, a study deviation will be given.
- If subjects do not follow the fingerstick recommendations or upload devices perfectly, no study deviation will be given unless the site staff did not train the subject on SMBG study procedures or upload procedures.

# 9.10.1. Documenting Requirements for Study Deviations

# 9.10.1.1. Unplanned CIP Deviations

The investigator may encounter the need to deviate from the CIP when necessary to protect the safety, rights or well-being of a subject in an emergency or in unforeseen situations beyond the investigator's control (e.g. subject failure to attend scheduled follow-up visits, inadvertent loss of data due to computer malfunction, inability to perform required procedures due to subject illness).

All deviations from the CIP, regardless of the reason should be documented as soon as possible, after the deviation occurs or is identified. This documentation should include deviation date, description of the deviation, and the reason for deviation.

CIP deviations should be reported as follows:

- a) To the IRB for notification/acknowledgement;
- b) To the sponsor and, if required;
- c) To the applicable regulatory agency (reported by the sponsor)

For medically justifiable conditions that preempt a subject's ability to complete a study-required procedure, it may be permitted to report only one deviation that will apply to all visits going forward. This may also apply to other unforeseen situations (e.g. the subject permanently refuses to complete a study required procedure and the data will not contribute to the primary end point analysis). However, prior approval from sponsor is required for such situations.

# 9.10.1.2. Minor or Administrative CIP deviations

Minor or administrative deviations are those that do not "affect the scientific soundness of the research plan or the rights, safety, or welfare of human subjects."

Deviations that do not meet the criteria for expedited notification or prior regulatory/IRB approval, may be reported at the time of eCRF completion or separately upon discovery such as during monitoring visits.

If a CIP deviation occurs which meets this definition, the deviation should be reported to the IRB at the time the continuing review application is submitted.

10813115DOC

Version D

Page 67 of 118

# 9.10.2. Reporting Requirements for Study Deviations

All study deviations must be reported on the eCRF regardless of whether medically justifiable, an inadvertent occurrence, or taken to protect the subject in an emergency. The date and reason for each deviation will be documented (21 CFR 812.140 Records). In the occurrence of a corrupted device interrogation file, Sponsor may request a deviation to document that a readable interrogation file is unavailable.

In order to protect the rights and interests, safety and health of subjects, the deviation occurred under emergency situations that cannot be timely reported shall be reported in written form afterwards in accordance with relevant regulations as soon as possible.

The following examples are deviations that could impact subject safety, affect the integrity of study data and/or affect subject's willingness to participate in the study. These deviations are significant and require immediate sponsor notification upon investigator awareness.:

- Failure to obtain informed consent/assent, i.e., there is no documentation of informed consent
- Informed consent/assent obtained after initiation of study procedures
- Continuation of a subject who did not meet all inclusion/exclusion criteria
- Performing study procedure not approved by the IRB
- Failure to inform IRB and sponsor of reportable AEs (see Section 11)
- Investigational study device dispensed without obtaining informed consent/assent

In the event the deviation involves a failure to obtain a subject's consent, or is made to protect the life or physical well-being of a subject in an emergency, the deviation must be reported to the IRB as well as Medtronic within five (5) working days.

Reporting of all other study deviations should comply with IRB policies and/or local laws and must be reported to Medtronic as soon as possible upon the center becoming aware of the deviation. Reporting of deviations must comply with IRB policies, local laws, and/or regulatory agency requirements. Refer to Investigator Reports, Table 5, for specific deviation reporting requirements and timeframes for reporting to Medtronic, IRB, and regulatory agency (if applicable).

# 9.10.3. Analyzing Deviations

Medtronic is responsible for reviewing deviations, assessing their significance, and identifying any additional corrective and/or preventive actions (e.g. amend the CIP, conduct additional training, terminate the investigation). Repetitive or serious investigator compliance issues may result in initiation of a corrective action plan with the investigator and investigational center, and in some cases, necessitate suspending enrollment until the problem is resolved or ultimately terminating the investigator's participation in the study.

# 9.11. Subject Exit, Withdrawal or Discontinuation

Subjects may choose to withdraw from the study at any time by notifying investigational center staff of their intent.

CIP321 Clinical Investigation Plan				
10813115DOC	Version D	Page 68 of 118		Medtronic

If a subject chooses to end his or her study participation or if the subject is removed from the study at the Investigator's discretion or for failure to meet the study requirements, the reason for withdrawal must be documented both in source documents and on the Exit eCRF. All study devices and supplies must be returned (as applicable) and documented both in source documents and on an eCRF.

A subject will be withdrawn from the study if:

- In the opinion of the investigator, the subject's health or safety would be compromised by continuing in the study
- In the opinion of the investigator, it is in the subject's best interest to discontinue • participation in the study
- During the study, subject begins using hydroxyurea. •
- During the course of the study, subject begins participation in another investigational study (drug or device).
- During the study it becomes known that subjects are using own SMBG or system that • replaces SMBG
- During the course of the study, subject begins abusing illicit drugs or marijuana. •
- During the course of the study, subject begins abusing prescription drugs.
- During the course of the study, subject begins abusing alcohol.
- During the course of the study, subject begins using pramlintide (Symlin), DPP-4 inhibitors, liraglutide (Victoza or other GLP-1 agonists), metformin, canagliflozin (Invokana or other SGLT2 inhibitors).
- During the course of the study, subject receives red blood cell transfusion or erythropoietin. •
- During the course of the study, the subject demonstrates that he/she is not able to comprehend instructions for study procedures, as evaluated by the appropriate research staff.
- During the study, a subject repeatedly activates SmartGuard™ when instructed otherwise, e.g. Auto Mode is turned on (as applicable)
- During the course of the study, subject is taking oral, injectable, or IV glucocorticoids
- During the study, (female) subject becomes pregnant.
- During the study, the subject experiences one severe hypoglycemic episode ٠
- During the study, the subject experiences one episode of DKA
- During the study, subject has a cardiovascular event or any vascular event such as stroke.

Documentation of the reason(s) leading to subject withdrawal will be kept in the subject's source file.

10813115DOC

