#### **Regular Sized Dinner Challenge with Missed Meal Bolus:**

On the day prior to attending Visit 5, while subjects are in manual mode with CGM, they will be asked to consume dinner without administration of a Meal Bolus. The size of the meal should be their standard amount. Subjects will be asked to check BG at the start of the meal, as well as 2 hours and 4 hours after the meal and provide correction as necessary. Content and timing of the meal, along with BG values, will be recorded on the Meal Challenge log. This missed dinner bolus challenge should only start if the following conditions are met:

- SMBG at start of meal is  $\leq$  200 mg/dL
- Sensor glucose is available.

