# 7.2. Subject Enrollment

Subjects will be considered enrolled in the study upon signing the Informed Consent Form (ICF)/ Assent Form.

A subject will be assigned a unique study subject ID (SID) via the eCRF, which is a 9-digit code (321XXXXX). The first three numbers refer to the CIP number (321), the next three numbers refer to the investigational center number, and the last 3 numbers refer to the subject number assigned during Visit 1 (e.g., 321002001 is subject 001 from site 002).

The investigator will maintain a log of all subjects enrolled in the clinical study, assigning a SID linked to their names, alternative SID, and contact information.

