# 9.12. Stopping Rules

### 9.12.1. Subject Stopping Rules

Any event of DKA or severe hypoglycemia will result in withdrawal of subject from study, if it is related to the use of AHCL Auto Mode.

Version D

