#### **11.3. Reporting of Adverse Events**

The investigator or designee will record ALL AEs while the subject is enrolled in the clinical study.

Each AE needs to be assessed for its device or procedure relatedness. A device related AE is associated with the use of the study device (e.g. infection of sensor site or infusion set occlusion resulting in DKA). A procedure related AE is associated with testing related to the study procedures specified in the CIP (e.g. IV insertion pain).

Examples of device or procedure related AEs include:

- *Device* related (ADE): insertion site infection
- Serious adverse *device effect*: cellulitis at device insertion site requiring hospitalization
- *Procedure* related AE: bruising at IV insertion site

Subjects participating in the study have diabetes and are expected to experience hypoglycemia and or hyperglycemia. These normal events are not expected to be reported to sponsor as this is not considered an untoward event, but rather an expected occurrence. Any glycemic excursion that meets the protocol definition of Severe Hypoglycemia, Severe Hyperglycemia or DKA is considered an untoward event and a worsening from the subject's baseline and would be reported to sponsor on an AE eCRF.

Baseline medical conditions should only be reported to sponsor on an AE eCRF if there is a worsening from the subject's baseline. For example, a subject previously diagnosed with Asthma is hospitalized for severe asthma attack would be a reportable event.

Adverse events will be documented in the subject source file and reported to sponsor on an eCRF. The investigational center is responsible for documentation of AEs including obtaining source documents related to the event, such as emergency medical technician/paramedic reports, hospital records (admission summary; lab results, test results, discharge summary) or device uploads to support the event. Source documents will be reviewed to determine if additional AEs have occurred and require reporting.

CIP321 Clinical Investigation Plan				
10813115DOC	Version D	Page 80 of 118		Medtronic

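### Protocol 9.11 and 9.12.1 give withdrawal rules of different scope after severe hypoglycaemia or DKA, and the DMC section plans a control-arm summary that a single-arm study cannot produce

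*Protocol*

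**What the plan says.** **Withdrawal.** The list in Protocol 9.11 opens with "A subject will be withdrawn from the study if" and includes "During the study, the subject experiences one severe hypoglycemic episode" and "During the study, the subject experiences one episode of DKA". Neither entry mentions cause. Protocol 9.12.1 also prescribes withdrawal after DKA or severe hypoglycaemia, but adds "if it is related to the use of AHCL Auto Mode". The synopsis row on subject stopping rules carries the same condition.

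**DMC summary.** Directly after Table 4, Protocol 12.2 announces a descriptive, unpowered summary of severe hypoglycaemia and DKA rates. It sets HCL against control arms, for ages under 15, 15-25 and over 25 and overall. Protocol 5 and SAP section 5 describe a single-arm study.

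**Reference rates.** Item a of the DMC guidance in Protocol 12.2 says, without exception, that the type 1 diabetes registry rates exceed those of STAR 3 and the two 530G in-home studies. Item b explains why the trial rates are lower. Item c points the DMC to the trial rates in Table 4 as the comparison for considering a stop.

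**The concern.** The withdrawal texts differ in scope for two central safety events. For an event unrelated to Auto Mode, 9.11 compels withdrawal; 9.12.1 and the synopsis do not. Nothing says which text governs. A site that follows the synopsis or 9.12.1 can in good faith keep a subject and so deviate from 9.11, because Protocol 9.10 treats any failure to follow the plan as a deviation.

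The age-band summary matters because it is the only planned display of observed rates in the bands used by Table 4, and it cannot be produced as worded. Item a matters less. It tells the DMC that the trial rates are the lower ones, yet above 25 years the two STAR 3 severe hypoglycaemia rates are the highest in their column.

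**Working it through.** **1. Do the withdrawal texts differ for events that this study can produce?**

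| Event | 9.11 | 9.12.1 and synopsis |
|---|---|---|
| Related to Auto Mode | withdraw | withdraw |
| Not related to Auto Mode | withdraw | no instruction |

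The second row is not empty. The protocol itself supplies two kinds of case.

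- *Run-in events.* Under 7.2, "Subjects will be considered enrolled in the study upon signing the Informed Consent Form", so the run-in is part of participation. In 9.3, Visit 3, "System is used in manual Mode by subjects who are not using Auto Mode with 670G at Screening". For the missed-bolus dinner on the day before Visit 5, section 5 says that "while subjects are in manual mode with CGM, they will be asked to consume dinner without administration of a Meal Bolus". Users of 670G Auto Mode may stay in that mode for the rest of run-in, but the meal-challenge table has them switch it off at least 6 hours before the dinner.
- *Infusion-set events.* Section 11.3 gives "infusion set occlusion resulting in DKA" as an example of a device-related event. Such an event need not be related to Auto Mode.

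**Which recorded assessment would decide the condition?** The investigator's five categories (11.6) and the CEC's three (12.1) both grade relatedness to the device or procedure. Factor 1 in 12.1 asks about the algorithm, but to inform the CEC's recommendation to the sponsor. Factor 4 refers to the CEC's final determination of causality for the AHCL System. None of these is named in 9.12.1, and none is graded against Auto Mode as such.

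**2. Can the summary after Table 4 be produced?** It needs a control arm, and Protocol 5 provides none. Other places that could supply the same display:

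- Protocol 12.2, first DMC function: severe hypoglycaemia and DKA rates per 100 patient-years, with no age bands.
- SAP 7.10: incidence over all enrolled subjects.
- SAP 7.2.1: age subgroups 7-13 and 14-75 only.

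The rates themselves therefore reach the DMC by another route. Only their tabulation in the Table 4 age bands depends on the faulty sentence.

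**3. Does Table 4 support item a?** Each trial rate was compared with the registry rate for the same event and age band (events per 100 patient-years).

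| Event, age | STAR 3 SAP arm | STAR 3 control arm | 530G study | Registry | Registry higher |
|---|---|---|---|---|---|
| DKA, >25 | 0.68 | 0 | 1.27 | 4.8 | 3 of 3 |
| DKA, 15-25 | 2.7 | 3.6 | 3.4 | 9.9 | 3 of 3 |
| DKA, <15 | 2.2 | 0 | 0 | 9.9 | 3 of 3 |
| Severe hypoglycaemia, >25 | **16.5** | **20.9** | 0.85 | 11.8 | 1 of 3 |
| Severe hypoglycaemia, 15-25 | 5.4 | 3.9 | 0 | 6.2 | 3 of 3 |
| Severe hypoglycaemia, <15 | **10.2** | 3.6 | 1.42 | 6.2 | 2 of 3 |

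DKA: 9 of 9 agree with item a. Severe hypoglycaemia: 6 of 9. Total: 15 of 18, with 3 exceptions, all from STAR 3. The ratios of trial to registry rate are 16.5/11.8 = 1.40, 20.9/11.8 = 1.77 and 10.2/6.2 = 1.65.

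**The case against.** **Withdrawal.** The best defence is that 9.12.1 states a sufficient condition, not a necessary one. It never permits continuation, 9.11 is mandatory, and a site that always withdraws obeys everything. That stands. A reader might infer that the rules cannot both be followed, or that 9.12.1 authorises keeping a subject after an unrelated event; the wording supports neither. Keeping such a subject breaches 9.11 whichever section the site had in hand. What remains is a condition with no effect, placed in the two texts a site is likely to consult for stopping rules. Other safeguards also stand: the investigator may withdraw a subject on safety grounds (9.11), the CEC reviews every severe hypoglycaemia and DKA (12.1), and the study-level rule (9.12.2) is untouched.

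**DMC summary.** A reader might infer that the DMC is left without usable safety rates. It is not: 12.2 gives it both rates per 100 patient-years, and item d lets it consider age. The summary is labelled as unpowered and no decision rule hangs on it. One might also take the control arm to be that of STAR 3, which Table 4 does contain, but the sentence does not say so.

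**Item a.** The sentence is right in 15 of 18 comparisons. The guidance is advisory and urges caution, item c directs the DMC to the table rather than to item a, and the committee includes a statistician. This limits the point to a correction of one sentence.

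**Size.** It is tempting to multiply the Table 4 rates by planned exposure and offer the result as the number of subjects affected. That would count all severe hypoglycaemia and DKA, not the part unrelated to Auto Mode. The predecessor paediatric study described in Protocol 3.1 reported no episode of either, so such a calculation has no firm lower bound. A precision argument from zero observed events would hold only for an assumed exposure and has no bearing on the wrong arm label.

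**Conclusion.** The concern holds as a set of internal inconsistencies, all curable by wording.

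1. *Main point.* Protocol 9.11 is broader than 9.12.1 and the synopsis. They can be obeyed together only by making the Auto Mode condition redundant. The affected events are those unrelated to Auto Mode. Their number cannot be derived from the documents, and none is claimed here.
2. *Second point.* The planned comparison with control arms cannot be carried out. The loss is confined to the display by Table 4 age band.
3. *Minor point.* Item a fails in 3 of 18 comparisons, by ratios of 1.40 to 1.77, and is correct for DKA throughout.

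Points 1 and 2 should be fixed; point 3 can go in the same amendment. The conclusion rests on reading 9.11 as mandatory, as its lead-in says, and on taking the Table 4 figures as printed. It implies no effect on power or on the day-90 analyses.

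**What to change.** 1. Reconcile Protocol 9.11, 9.12.1 and the synopsis so that one withdrawal rule stands in all three. This review takes no view on which rule is right. The text should state whether the rule depends on causality; if so, which recorded assessment decides it; and whether it covers the run-in.
2. In 12.2, after Table 4, replace the comparison with control arms by observed AHCL events, accrued patient-years and the rate per 100 patient-years for <15, 15-25, >25 years and overall, shown beside the Table 4 reference rates. An exact Poisson interval and a copy of the table in SAP 7.10 are optional.
3. Limit item a to DKA and add the exceptions: for severe hypoglycaemia, STAR 3 exceeds the registry above 25 years in both arms and below 15 years in the SAP arm.

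The cost is a few sentences in Protocol 9.11, 9.12.1, 12.2 and the synopsis, and at most one table shell. No added data or subjects are needed.
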